The primary hypothesis is that lithium is superior to placebo for the prevention of episodes of suicidal self-directed violence, including suicide attempts, interrupted attempts, hospitalizations to prevent suicide, and deaths from suicide over the ensuing year. The primary outcome measure is time from randomization for treatment allocation to the first episode. The results for event-free survival will be analyzed by means of a two-sided log-rank test. The study will have one interim analysis and one final analysis.

The duration of the study will be 4.5 years total, which allows for 3 years of recruitment, 1 year of follow-up for all enrollees, and time for start-up and closeout as indicated. A total of 1,862 patients will be enrolled and randomized to receive either lithium or placebo, both in addition to

enhanced usual care. We expect to enroll an average of 65 patients per site at 29 VA medical centers. All subjects will be followed for 12 months after randomization. Section IX describes site identification and recruitment plans.

Estimated Incidence of Primary Endpoint

We posit a 1-year event rate of 15% in the placebo group for the primary outcome based on data from the literature on lithium and SPAN data.

Lauterbach et al. (2008) reported a 12% 1-year reattempt rate in the placebo group in a cohort primarily of women, slightly younger than the VA cohort, and predominantly with major depressive disorder. This rate is slightly lower than that projected for the current study possibly because hospitalizations to prevent suicide were not included. Oquendo et al. (2011) evaluated suicide attempts and suicide events separately. Reattempt rates at 1 year were approximately 12% and 18% in the lithium and valproate groups respectively. In spite of their small samples and a more rigid definition of the endpoint, these two trials provided point estimates of outcome event rates between 12% and 18%.

To obtain a more precise estimate of the event rate in the Veteran population, we used VA SPAN data from second half of FY 2010 through the first half of FY 2012 (24 months), to characterize the target Veteran population potentially eligible for the proposed study. Detailed analysis of this cohort is presented in Section IX and selected characteristics of this target population are included and compared to the participant profiles of prior studies in Table 2.

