Both stratification and blocking will be utilized to control for potential imbalances in randomization. The randomization scheme will be stratified by participating site in addition to diagnosis (bipolar vs. depression) and history of prior attempts other than the index attempt (none vs. 1+ attempt). Stratification by site is necessary because of possible regional differences in clinical practices. Participants will be randomized to either lithium or placebo within permuted random blocks of 4 so that the treatment arms are balanced after every 4th randomization within the 4 strata at each site: bipolar with prior attempt, bipolar without prior attempt, depression with prior attempt, and depression without prior attempt. Breaking the blind at the end of each participant's time in the study is not expected to provide information about the treatment assignment of participants remaining in the study as block randomization is within multiple strata. Regardless, an extra treatment assignment will be inserted to each stratum of four to disrupt the blocks and make block size harder to discern.

A web-based randomization program validated by the MAVERIC CSPCC will be provided to study sites. At subject enrollment, Site Coordinators will enter the patient ID number, study site, and eligibility information into the randomization program to confirm that all eligibility criteria are met. If met, the program will select the first unused entry from the pre-specified list of random treatment assignments for the particular site. The lists will be stored on a secure server at MAVERIC CSPCC. In case the electronic system is down, the identical process can be followed manually and the randomization scheme telephoned or faxed to the site.

This CSP clinical trial is a double-blinded study in which neither the patient nor the site investigator knows to which of the two study arms the patient has been assigned. Emergency drug code envelopes will be prepared by the CSPCRPCC and shipped with the study drugs to the Pharmacy Service of the participating medical center prior to the study starting. Each envelope is numbered with a unique patient randomization number and contains the treatment assignment for

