4.3. Statistical Methods for Primary Efficacy Analysis

Primary efficacy analysis will include the modified intention to treat sample as defined in section 3.3 above.

The primary hypothesis can be stated as follows.

Under the null hypothesis: The 1-year event rate is 15% and the two treatment groups do not differ in their time to event hazard rates.

Under the alternative hypothesis: The 1-year event rate is 9.45% for patients treated with lithium and 15% for patients in the placebo group, resulting in an absolute reduction from 15% to 9.45% = 5.55% and a relative reduction of $(15 - 9.45)/15 = 37\%$. The group on lithium augmentation has a lower hazard rate than the placebo augmentation group with a hazard ratio for lithium therapy compared to control therapy lower than or equal to 0.61.

We will test this hypothesis with a two sided log rank test at 90% power and 4.8% Type I error (i.e., 5% overall error allows for one interim test at 0.2%). Null hypothesis will be rejected if the hazard ratio exceeds $1/0.61 = 1.64$ or falls below 0.61.

A significant difference showing that the lithium augmentation compared to placebo decreases the hazard of suicidal self-violence will be regarded as a positive result, whereas a result that shows lithium augmentation does not significantly differ from placebo or significantly increases the hazard rate relative to placebo will be regarded as a negative result.

Log rank test will be followed by Cox proportional hazards regression modeling to provide the hazard rates, their ratio and the 95% confidence interval about the ratio.

We will test the proportional hazards assumption by including a time*treatment interaction term in the model and use graphic methods to study goodness of fit as described in Anderson et. al., 1991.

The SAS code for the primary analysis is as follows, where, tx is coded as {1=lithium, 0=placebo}, event is coded as {1=adjudicated outcome, 0=otherwise}, and FUdays is counting number of days from randomization date to the first occurrence of (adjudicated outcome, death, 12 month date, or last study visit/contact date).

Log-Rank Test:

```
title "Survival Estimates by Month";
proc lifetest data=endpt plots=(s); time FUdays*event(0); strata tx; run;
quit;
proc lifetest data=endpt method=life plots=(ls) intervals=30 90 120 150
180 210 240 270 300 330 365; time FUdays*event(0); strata tx; run; quit;

title "Survival Estimates by Month";

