proc lifetest data=endpt method=life plots=s intervals=30 90 120 150 180
210 240 270 300 330 365; time FUdays*event(0); strata tx; run; quit;

title "Hazard Estimates by Month";
ods output lifetableestimates=life(keep=stratum lowertime uppertime
hazard);
proc lifetest data=endpt method=life intervals=30 90 120 150 180 210 240
270 300 330 365; time FUdays*event(0); strata tx; run; quit;
data life; set life; where hazard ne .;
time=lowertime+(uppertime-lowertime)/2; keep stratum time hazard; run;
proc export data=life outfile="life.csv" dbms=CSV replace; run;

title "Basic model - Exponential";
proc lifereg data=endpt; model FUdays*event(0)=tx5fu / dist=exp; run;
quit;
```

Cox-Proportional Model:

```
*CHECK PROPORTIONAL HAZARDS FOR TREATMENT*;
title 'Basic model - Cox model with treatment*time interaction';
ods select ParameterEstimates;
proc phreg data=endpt; where FUdays>0;
```

```

    model FUdays*event(0)=tx int/ rl;
    int=tx*log(FUdays);
    Proportionality: test int;
run; quit;

proc phreg data=endpt; where FUdays>0;
    model FUdays*event(0)=tx;
    output out=propcheck ressch=schres;
run; quit;
proc sgplot data=propcheck; loess x=FUdays y=schres / clm; run;

title "Basic model - Cox model";
proc phreg data=endpt; model FUdays*event(0)=tx / rl;
run; quit;

```

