4.4. Evaluating Covariate Effects and Heterogeneity by Site

First, we will identify potential confounding factors that are not balanced between the intervention groups and evaluate the possibilities of treatment by covariate effects. This will be done by refitting the primary cox proportional hazard model with a vector of covariates included in the model.

We will also fit a random effects or frailty model to investigate potential heterogeneity of effect due to site variability. This will be accomplished by refitting the primary cox proportional hazard model with additional classification and random statements.

```

title "Random Effects - Cox Model";
proc phreg data=endpt;
class site tx;
model FUdays*event(0)=tx / rl;
random site;
hazardratio "Frailty Model Analysis" site;
run; quit;

```

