4.5. Sensitivity Analysis

The primary efficacy analysis will be repeated under 3 different scenarios as follows.

- (1) Randomization was stratified on two factors: (1) Bipolar or Major Depressive Disorder diagnosis, and (2) prior history of suicide attempt. Cox Regression Model as described in section 4.3 will be refitted with the inclusion of diagnosis variable and suicide history variable in the model.
- (2) Primary efficacy analysis will be repeated on the “per-Protocol” sample with adherence as defined in section 3.4 to evaluate efficacy among those adherent to the protocol.
- (3) Primary efficacy analysis will be repeated on the modified ITT analytic cohort that excludes all randomized subjects who terminated prior to the first titration visit.

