10.1. Interim Analysis

We will conduct one interim analysis after half of the participants have completed their 12 month follow up. This analysis is projected to take place approximately 2.5 years after initiation of enrollment (assuming it will take 1.5 years to enroll half the sample and allow 12 months of follow-up). After adjusting for attrition, a sample of 746 evaluable subjects, (373 in each group), is expected to be included in the analysis.

Projecting the same event rate in this sub-sample we expect to observe a 15% or 112 events (56 events in each group) under the interim null hypothesis that event rates are equal in the treatment groups. Under the interim alternative hypothesis, the absolute reduction from 15% to 5.3% is $(15-5.3) = 9.7\%$, the relative reduction is $(15-5.3)/15 = 65\%$, and the hazard ratio (treatment hazard rate/control hazard rate) is 0.34. The interim log-rank test is two-sided, and the interim null hypothesis will be rejected if the hazard ratio exceeds $1/0.34 = 2.94$ or falls below 0.34. Using the O'Brien-Fleming procedure, (Turnbull & Jennison, 2000), this analysis will have a Type I error of 0.2%.

We will confer with the Data Monitoring Committee members and the program leadership for potential stopping guidelines based on results from interim efficacy analysis.

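### The primary log-rank test and Cox model use none of the randomisation strata: stratifying by diagnosis and prior attempt is a small, free improvement, and SAP 4.5 wrongly omits site as a stratification factor

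*SAP*

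**What the plan says.** Protocol section VII, Randomization Plan: "The randomization scheme will be stratified by participating site in addition to diagnosis (bipolar vs. depression) and history of prior attempts". Blocks of 4 are used within four diagnosis-by-history strata at each site. The reason given for the site factor is: "Stratification by site is necessary because of possible regional differences in clinical practices".

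SAP 4.3 gives the primary log-rank code as "proc lifetest data=endpt plots=(s); time FUdays*event(0); strata tx; run" and the primary Cox model as "proc phreg data=endpt; model FUdays*event(0)=tx / rl". The protocol's Overview in section VII is equally plain: "The results for event-free survival will be analyzed by means of a two-sided log-rank test". Neither document plans a stratified log-rank test.

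The stratification factors appear in two supplementary places:
- SAP 4.4 handles site through a frailty model, obtained by "refitting the primary cox proportional hazard model with additional classification and random statements". The same section adds covariates that turn out to be unbalanced between the arms.
- SAP 4.5(1) refits the Cox model with diagnosis and suicide history. It introduces this with "Randomization was stratified on two factors: (1) Bipolar or Major Depressive Disorder diagnosis, and (2) prior history of suicide attempt".

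SAP 10.1 says of the interim test only that "The interim log-rank test is two-sided", apart from its error level and rejection limits. It does not say whether that test is stratified.

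**The concern.** In PROC LIFETEST, a lone `strata tx` defines the groups being compared. The decision-making test is therefore unstratified, although the design balances the arms within site, diagnosis and history. When such factors predict outcome, ignoring them makes the log-rank test slightly conservative and leaves prognostic information unused.

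The imbalance rule in SAP 4.4 does not fill this gap. Factors balanced by design will rarely be flagged as unbalanced. Model 4.5(1) does use two of the factors, but only as a sensitivity analysis.

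At stake is a little efficiency in the primary and interim tests. Separately, SAP 4.5 misdescribes the randomisation: it counts two factors, and the protocol has three.

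**Working it through.** **The plan's own figure.** Inputs from SAP 4.3 and 10: event rates of 15% and 9.45%, 745 evaluable per arm, final two-sided alpha 0.048.
- Events: 745 × (0.15 + 0.0945) = 182.2. The plan has 182.
- Hazard ratio (HR): ln(1 - 0.0945) / ln(1 - 0.15) = 0.611. The plan has 0.61.
- Schoenfeld power: Φ(√182 × |ln 0.61| / 2 - 1.977) = Φ(1.357) = 91.3%.
- Freedman power: Φ(√182 × 0.39 / 1.61 - 1.977) = Φ(1.291) = 90.2%.

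The stated 90% therefore reproduces for the unstratified test.

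**Anchors for prognostic strength.** The documents give no event rates by stratum. Protocol section I offers two indirect guides. About half of attempters were first-time. Suicide death rates were 113 per 100,000 in bipolar disorder and 82 in depression, a ratio of 113/82 = 1.38. That ratio concerns deaths, not this endpoint.

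**Main simulation.** 20,000 trials per setting, with both tests applied to the same data. From the documents: 1862 patients, 29 sites, blocks of 4 within site × diagnosis × history, 40% dropout, placebo risk 15%, within-stratum HR 0.611, alpha 0.048. Assumed: equal sites, uniform dropout, 25% bipolar, 50% with a prior attempt, and the prognostic strengths shown. It yields 183 to 185 events under the alternative.

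| Prior-attempt HR / diagnosis HR | Site SD (log-hazard) | Unstratified | Four strata | Difference, points (Monte Carlo SE) |
|---|---|---|---|---|
| 1 / 1 | 0 | 90.4% | 90.4% | -0.04 (0.04) |
| 1.5 / 1.2 | 0 | 90.7% | 90.8% | +0.10 (0.05) |
| 2 / 1.5 | 0 | 90.5% | 90.9% | +0.36 (0.07) |
| 3 / 1.5 | 0 | 90.0% | 90.6% | +0.64 (0.08) |
| 1 / 1 | 0.5 | 89.9% | 89.9% | -0.01 (0.04) |
| 2 / 1.5 | 0.5 | 89.5% | 89.8% | +0.30 (0.07) |
| 3 / 1.5 | 0.5 | 88.8% | 89.5% | +0.69 (0.09) |

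With diagnosis HR at 1.38, the gains are:
- +0.03 (0.05) with prior-attempt HR 1 and no site effect;
- +0.12 (0.05) with prior-attempt HR 1.5 and site SD 0.3;
- +0.17 (0.06) with prior-attempt HR 2 and site SD 0.3.

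**Second simulation.** 6,000 trials per setting, 20% bipolar, site SD up to 0.3. The change ranges from -0.1 points (90.8% to 90.7%, no prognostic effect) to +0.7 points (90.8% to 91.5%, prior-attempt HR 3, diagnosis HR 1.5).

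**Type I error against 4.8%.** Main simulation: 4.1 to 4.9% unstratified and 4.3 to 4.9% with four strata. At site SD 0.5 these become 4.1 to 4.4% and 4.3 to 4.6%. Second simulation: 4.4 to 5.2% and 4.5 to 5.2%, with Monte Carlo SE about 0.3 points.

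**Interim.** Under the design alternative, 373 × (0.15 + 0.0945) = 91 events are expected; the simulation, with 931 randomised, gives about 92. At two-sided 0.002, power goes from 21.5% to 21.5% (no effects), 20.9% to 21.6% (prior-attempt HR 2, site SD 0.3) and 19.1% to 20.4% (prior-attempt HR 3, site SD 0.5). The smallest of the four strata holds about 8 to 14 interim events.

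**Why not stratify by site as well.** 29 × 4 = 116 cells leave 1862/116 = 16 patients and 182/116 = 1.6 events per cell. In the main simulation, full stratification loses 0.74 points (0.11) against the unstratified test when nothing is prognostic. It never beats four strata, even at site SD 0.5 with prior-attempt HR 3 (89.3% against 89.5%). In the second simulation it falls 0.4 to 1.3 points below the unstratified test.

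**The case against.** The strongest reply is that this is a preference. Both documents consistently specify a plain log-rank test, and the 90% power was computed for it. The adjusted and frailty models already let a reader see whether the strata move the HR. All of that is true, and it is why the severity is low. It does not explain why factors chosen for randomisation should be left out of the primary test when using them costs essentially no power.

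The size of the gain can also be challenged, and this stands. The top of the range needs an assumed prior-attempt HR of 3. The 1.38 ratio comes from deaths among all VHA patients. The accompanying counts imply a bipolar share of about (110/113) / (110/113 + 400/82) = 17%, below the shares simulated. The figure of about half first-time attempters precedes the exclusion of patients with six or more attempts.

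A third objection is that the change reaches beyond 4.3. This also stands. In a Cox model stratified by diagnosis and history, the two covariates added in 4.5(1) are constant within strata and drop out of the partial likelihood. Sections 4.4, 4.5(2), 4.5(3), 5.3 and 6.3 all build on 4.3.

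The interim gap is minor. SAP 4.3 defines only one log-rank test, so 10.1 is naturally read as meaning that one.

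A reader might infer that the primary test is invalid or underpowered, or that the headline HR is ambiguous. The documents support neither. The test holds its level and its power, and SAP 4.3, 4.4 and 11 make the treatment-only model primary. Nor does the protocol's remark that site stratification is needed show that site must enter the primary test. The remark concerns randomisation, and 116 sparse cells would give no more power than four strata.

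**Conclusion.** The point holds as a free improvement of low severity. The primary analysis uses none of the three randomisation factors. It is nonetheless valid, has about 90% power and is at worst slightly conservative. Four strata change final power by about -0.1 to +0.7 points. At the only ratio the documents offer for diagnosis, the gain is 0.03 to 0.17 points, and the upper part of that range still assumes prior-attempt and site effects. Interim power changes by about 0 to +1.3 points.

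Confidence is high in the reading of the code and in the smallness of the effect. The exact gain depends on prognostic strengths that the documents do not give. The match to the randomisation stays partial, because site remains outside the primary test.

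The two-factor statement in SAP 4.5 contradicts the protocol whatever is assumed. It changes no result, since site is modelled in 4.4.

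**What to change.** Make these changes before any unblinded efficacy comparison. After such a comparison, a change of primary test could look data-driven, and a gain this small would not justify it.

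1. In SAP 4.3, stratify the log-rank test by diagnosis and prior attempt (`strata dx prior / group=tx` in PROC LIFETEST) and use a matching stratified Cox model (`strata dx prior` in PROC PHREG). State in 10.1 that the interim test takes the same form.
2. Replace 4.5(1) with the present unstratified log-rank test and treatment-only Cox model as the sensitivity analysis.
3. State whether 4.4, 4.5(2), 4.5(3), 5.3 and 6.3 carry the strata. Align the protocol's section VII text on the primary test, the Cox model and the power basis.
4. Keep site in the 4.4 frailty model and give the reason: 116 cells with about 1.6 events each.
5. Correct 4.5 to list site as the third stratification factor.

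The cost is document editing, with no extra patients or data. The sample size can stand. With a within-stratum HR of 0.611, the overall HR is 0.611 to 0.617 with no site effect and 0.623 in the strongest site setting, against the planned 0.61.

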4.4. Evaluating Covariate Effects and Heterogeneity by Site

First, we will identify potential confounding factors that are not balanced between the intervention groups and evaluate the possibilities of treatment by covariate effects. This will be done by refitting the primary cox proportional hazard model with a vector of covariates included in the model.

We will also fit a random effects or frailty model to investigate potential heterogeneity of effect due to site variability. This will be accomplished by refitting the primary cox proportional hazard model with additional classification and random statements.

```

title "Random Effects - Cox Model";
proc phreg data=endpt;
class site tx;
model FUdays*event(0)=tx / rl;
random site;
hazardratio "Frailty Model Analysis" site;
run; quit;

```

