10.1. Interim Analysis	
10.2. Futility Analysis	
11. Final Statistical Report.....	page 24
12. References.....	page 25

1. Introduction

This document outlines the statistical methods for the analysis of data collected in the Department of Veterans Affairs Cooperative Studies Programs (CSP) study #590 entitled “A Randomized double-blind placebo-controlled trial of lithium augmentation and enhanced suicide prevention management in preventing suicide re-attempts in individuals with depression and bipolar disorder.” The purpose of this document is to provide guidelines from which the analysis will proceed. Deviations from these guidelines will be documented and filed electronically in the study central file Sharepoint site.

The following documents were used in preparation of this statistical analysis plan (SAP):

- Clinical Study Protocol CSP #590
- Case Report Forms (CRF) from above entitled Protocol
- Global CSP SOP 2.9: “Developing and Conducting Statistical Analyses
- Local Work Instruction WI 201Statistical Analysis Plan and Biostatistical Research Data Processing Plan Creation and Amendment
- Local Job Aid No. 5: Guide to Writing Statistical Analysis Plans

2. Overview of the Study Design and Study Objectives

This is a double-blind, placebo-controlled randomized clinical trial that will assess the effectiveness of lithium augmentation to enhanced usual care for prevention of repeated fatal and non-fatal suicide attempts in participants with bipolar disorder or depression who have survived a recent episode of suicidal self-directed violence.

A total of 1862 subjects recruited from 29 Veterans Health Administration (VHA) centers over a 3 year period are expected to be randomized equally to lithium (Lithium ER) or placebo. Participants will be followed actively for 12 months from randomization. Adverse event monitoring for safety will be for one additional month beyond active follow up, i.e., up to 13 months.

The primary hypothesis is that lithium is superior to placebo for the prevention of episodes of suicidal self-directed violence over time. The primary outcome measure is time from randomization for treatment allocation to any first episode of suicide attempt, interrupted attempt, hospitalization specifically to prevent suicide, or death from suicide.

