5.3. Statistical Methods for Secondary Analyses

Secondary objective#1 will use a time to event, survival analysis to determine whether there is a treatment difference in event rates for each of the defined endpoints. The null hypothesis for each endpoint is that the two treatment groups do not differ in their hazard

rates. The alternative hypothesis is that the intervention group on lithium has a lower hazard rate than the placebo group. As with the primary analysis, log-rank test and Cox proportional hazards models will be used.

For secondary objective#2, the null hypothesis for each of the factors is that treatment effect does not differ over levels of the factor. The alternative hypothesis is that there is differential treatment effect over levels of the factor. Effect modification will be evaluated through regression methods. Cox proportional hazards regression model will include the treatment term, a term for the target factor, and the interaction term of the two. If the null hypothesis is rejected at $p=0.05$ level, i.e., the interaction term in the model is statistically significant, separate regression models will be refitted for each level of the factor. A forest plot will be used to display the results.

For secondary objective#3, the null hypothesis is that total event rates do not differ by treatment assignment, and the alternative hypothesis is that there is a difference in total event rates across treatment groups. We will use Generalize Linear Models (glm), namely Poisson regression, to model cumulative total of endpoint events with an offset for follow up time.

For secondary objective#4, the null hypothesis is that change in symptoms and suicidal ideation in the lithium group is similar to that of the placebo group. The alternative hypothesis is that there is a difference in change across treatment groups over time. We will use Generalize Linear Models (glm), namely Logistic regression, to model presence or absence of symptoms and suicidal ideation at each follow up visit, while allowing for random effects of variation in symptoms of bipolar disorder and depression at baseline.

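### SAP 4.4: the site frailty model has only a random intercept, so it cannot support any statement about whether the lithium effect differs between sites

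*SAP*

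**What the plan says.** SAP 4.4 gives the aim: "We will also fit a random effects or frailty model to investigate potential heterogeneity of effect due to site variability". The Protocol (Section VII, Primary Data Analysis Plan) states the same aim, directly after the Cox model that yields the treatment hazard ratio, and gives no further specification.

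The method is in SAP 4.4: "This will be accomplished by refitting the primary cox proportional hazard model with additional classification and random statements". The code then has three working parts:

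- the fixed-effects line, "model FUdays*event(0)=tx / rl", with treatment (`tx`) as the only term;
- a random statement naming `site` alone;
- a contrast request, "hazardratio 'Frailty Model Analysis' site".

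Site matters by the plan's own account. It is a randomization stratum, and the Protocol's Randomization Plan says: "Stratification by site is necessary because of possible regional differences in clinical practices". For other factors, SAP 5.3 specifies heterogeneity in the usual way: "Cox proportional hazards regression model will include the treatment term, a term for the target factor, and the interaction term of the two". Site is not in the subgroup list of SAP 5.1, and SAP 4.5 adds only diagnosis and attempt history to the Cox model. The remaining by-site outputs are enrollment, form-completion, baseline and safety tables.

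**The concern.** The aim names heterogeneity of effect, but the model has no term through which the treatment effect could differ between sites. Anyone reading its output as evidence on that question would be relying on a quantity the model fixes at zero. The requested contrast does not help, because a hazard ratio for site compares sites' hazards with each other, not lithium with placebo within sites.

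The question is a reasonable one for this trial. Dose adjustment is left to Site Physicians; the Protocol (Section VIII, item G) records that central dose adjustment was considered and that its main advantage might have been less between-site variability in those decisions. At stake is whether a supportive statement about consistency across 29 sites could be justified. The primary conclusion is not at stake.

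**Working it through.** **1. What the coded model contains.** Written out, the log hazard for a patient at site s is

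log h(t) = log h0(t) + β·tx + b_s, where b_s is the random site intercept.

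The lithium/placebo hazard ratio within site s is exp(β + b_s) / exp(b_s) = exp(β). The site term cancels, so the ratio is identical at all 29 sites whatever the data show. The parameters are β and the variance of b_s; there is no variance for a site-specific treatment effect.

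**2. Design figures.** SAP 4.4 states no number to reproduce, so these are background.

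- Event rates (SAP 4.3): "The 1-year event rate is 9.45% for patients treated with lithium and 15% for patients in the placebo group".
- Hazard ratio = ln(1 − 0.0945) / ln(1 − 0.15) = 0.611, against 0.61 in the SAP.
- Events = 745 × (0.15 + 0.0945) = 182.2, against 182 in SAP Section 10.
- Power with 182 events at two-sided alpha 0.048, Freedman's formula: 90.0%, as stated.

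**3. Information per site.** There are 29 sites (SAP Section 2).

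- Events per site: 182 / 29 = 6.3.
- Placebo: 745 × 0.15 / 29 = 3.9. Lithium: 745 × 0.0945 / 29 = 2.4.
- Approximate sampling SE of one site's log hazard ratio: √(1/3.9 + 1/2.4) = 0.82.

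**4. Does the planned output respond to treatment-effect variation?** A small simulation compared the SAP's random-intercept model with one that adds a random treatment slope by site. It used exponential survival, one year of follow-up, 29 equal sites, 26 evaluable patients per arm per site, planned event rates and 60 runs per scenario. The between-site SDs (log-hazard scale) are assumptions; the documents give none.

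| True variation between sites | Intercept-only model: median site SD | Slope model: median treatment-by-site SD | Slope model: LR statistic above 2.71 |
|---|---|---|---|
| None | 0.01 | 0.01 | 7% |
| Baseline hazard only (SD 0.4) | 0.40 | 0.01 | 5% |
| Treatment effect only (SD 0.8) | 0.33 | 0.74 | 90% |
| Both (0.4 and 0.8) | 0.49 | 0.80 | 93% |

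The intercept-only model reports a similar site SD whether only baseline risk varies (0.40) or only the treatment effect varies (0.33). Nothing in its output tells the two apart. The slope model does separate them.

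**5. Scale of what could be at issue.** If site log hazard ratios had SD 0.4 around 0.61, the central 95% of site hazard ratios would be 0.61 × exp(±1.96 × 0.4) = 0.28 to 1.34. With SD 0.8 it would be 0.61 × exp(±1.96 × 0.8) = 0.13 to 2.93. Neither SD has a basis in the documents. At 0.4 the true SD is about half the sampling SE of a single site (0.82), and the simulation did not test detection at that size.

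**The case against.** **The aim is loosely worded.** The section title refers only to heterogeneity by site. The reason given for stratifying by site, regional practice differences, fits varying baseline risk. The two references that the Protocol attaches to the sentence carry titles about clustered and heterogeneous survival data, which suit a shared-frailty model. If baseline risk was meant, the random statement does its job and only the wording and the contrast line need correcting. This narrows the point. It does not remove it, because heterogeneity of effect in a sentence that follows the treatment hazard ratio most naturally means the lithium effect.

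**A reader might infer that the planned model would show nothing of any treatment-effect variation.** That is too strong. With only the treatment effect varying, the intercept-only model still returned a median site SD of 0.33. It absorbs part of the variation but cannot attribute it.

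**A reader might infer that the final report will claim a finding on site heterogeneity.** The documents do not say so. SAP Section 11 covers Section 4 in general, but its stated minimum content names the results of 4.3, not 4.4. SAP Section 1 describes the plan as guidelines, with deviations documented.

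**The contrast line is a small slip.** The fixed-effects line carries the same `rl` option as the primary Cox code, so the site-adjusted treatment hazard ratio is already requested. Whether the contrast line would run, given that site is not in the fixed-effects line, depends on software behaviour the documents do not describe; nothing here relies on it.

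**The remedy has limited power.** The 90% and 93% detection rates come from an assumed SD of 0.8. This stands.

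**Conclusion.** The coded model cannot deliver the aim as most naturally read. It yields a between-site variance in baseline hazard and a common, site-adjusted treatment hazard ratio, and it cannot support any statement, positive or negative, about site heterogeneity of the lithium effect. That follows from the model's form and needs no assumed SD. It does depend on reading effect as treatment effect, which the SAP should confirm.

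The size is small: one supportive analysis, no planned figure altered, and the design's 182 events and 90% power reproduced. How much heterogeneity might go unexamined cannot be derived from the documents; the ranges under SDs of 0.4 and 0.8 are illustrations only.

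**What to change.** 1. State in SAP 4.4 which heterogeneity is meant: baseline risk, treatment effect, or both.
2. Keep the shared-frailty model, replace the contrast on `site` with `hazardratio tx`, and label the result the site-adjusted treatment effect.
3. For treatment-effect heterogeneity, add either a random treatment effect by site (mixed-effects Cox) or a treatment-by-site-group interaction with low-enrolling sites pooled by a rule set before unblinding. Report the between-site variance of the log hazard ratio, or the interaction test, as descriptive.
4. Say beside the result that failure to detect heterogeneity does not show its absence.

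The cost is a few lines of code and text, with no new data and no change to the primary test, alpha or sample size. The downside is an imprecise estimate that may miss modest heterogeneity, given about 6 events per site.
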